7.6 Variables to be Measured to Demonstrate Achievement of Endpoints

The endpoints and additional measures will be assessed as described in Table 7.6-1.

Table 7.6-1. Assessment of Endpoints and Measures

Endpoint/Measure	Measure/Assessment
Use of adjunctive therapies	Procedural use of high-pressure balloons, cutting balloons, or stents following the study procedure (initial treatment with Enforcer or conventional angioplasty balloon)
Device success	Residual stenosis less than 30% within the treated lesion immediately after angioplasty with the study device (Enforcer or conventional angioplasty balloon)
Anatomic success	Residual stenosis less than 30% within the treated lesion following procedure (including any adjunctive therapy)
Procedural costs	Procedural charges and cost-to-charge ratio assessed after submission of UB-04 or CMS-1500 forms
Procedural time	Procedural time (defined as the time from needle entry for intervention to sheath withdrawal) will be assessed after angioplasty with the study device (Enforcer or conventional angioplasty balloon)
Balloon pressure	Maximum inflation pressure and duration
Numeric rating scale (NRS) for pain experienced during study procedure balloon inflations	Patient-reported pain assessment (scale of 0-10, where 0 indicates no pain and 10 indicates the worst possible pain)
Clinical success	Resumption of successful hemodialysis for at least one session from chart review through 90 days
Primary Patency	Uninterrupted patency of the AV hemodialysis access circuit assessed by reporting of reintervention or abandonment of dialysis

	access circuit from chart review through 90 days
Adverse events	Event information from chart review through 90 days 
Refer to Section 9.6: Adverse Events, for a list of reportable events

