9.1 Pre-procedure

A pre-procedural clinical assessment will be completed and will include patient demographics and medical history. Baseline data will be collected and recorded on appropriate eCRFs. Baseline angiography should be performed prior to study enrollment to assess and document study lesion(s) characteristics including length, location, and percent (%) stenosis. Up to two distinct lesions can be treated within the dialysis access circuit. Pre-treatment for thrombosed dialysis access circuits may be performed (e.g., thrombectomy or thrombolysis) prior to enrollment in the study. Also, central venous lesions that require treatment (i.e., >50% stenosis) to meet eligibility criteria must be treated successfully prior to treatment of the study lesion. Successful treatment of the central veins is defined as less than 30% residual stenosis.

Once baseline angiography is complete and patient eligibility is confirmed, patients will be randomized as described in Section 7.4.1 into either the Enforcer balloon or conventional angioplasty balloon (defined as balloons with rated burst pressure of less than 25 atm) group prior to treatment.

Assessment(s) required to be completed prior to patient enrollment are summarized in Table 9.1-1.

Table 9.1-1. Pre-procedure requirements

Pre-procedure	
Assessment(s)/ Procedure(s)	Review study with the patient and obtain written informed consent
	Record demographics, medical history, and AV fistula/graft location
	Perform pre-procedural (baseline) angiography, recording lesion characteristics such as:
	
• Lesion length, location, and % stenosis• Estimated reference vessel diameter
	If necessary, perform treatment of central venous stenosis, confirming residual stenosis less than 30%
	If necessary, perform pre-treatment for thrombosed access circuit
	Confirm ability to cross the study lesion(s) with a guidewire
	Randomize patient

If a subject does not qualify for study participation, the reason will be indicated on the appropriate eCRF.

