9.2 Point of Enrollment

Patients are considered enrolled in the study once the balloon catheter is first introduced into the patient's body.

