9.3 Study Procedure

PTA with either the Enforcer balloon or conventional angioplasty balloon will be performed and recorded in accordance with the manufacturer's IFU to achieve a residual stenosis < 30%. The balloon diameter may be chosen based on the recommendations in the IFU. If necessary, the balloon could be deflated, repositioned, and re-inflated to achieve a residual stenosis < 30%. Inflation details (e.g., maximum pressure and duration of inflations) will be recorded on an appropriate eCRF. Conventional angioplasty balloons are defined as those having a rated burst pressure less than 25 atmospheres. Completion angiography to assess percent residual stenosis of the treated study lesion(s) should be performed immediately following the study procedure (initial treatment with Enforcer or conventional angioplasty balloon) and prior to beginning any adjunctive procedures.

The physician may also perform adjunctive procedures (e.g., using a high-pressure balloon, cutting balloon, stent, or stent graft) if in the best interest of the patient. High-pressure angioplasty balloons are defined as those having a rated burst pressure greater than or equal to 25 atmospheres. The adjunctive procedure may be performed in accordance with the device manufacturer's IFU to achieve a residual stenosis < 30%. Completion angiography following any adjunctive procedures should also be performed. Any additional procedures performed will be documented on the appropriate eCRF.

All angiographic images and medical charges (i.e., UB-04 or CMS-1500) should be provided to the Sponsor on the appropriate eCRF. Total procedure time (defined as the time from needle entry for intervention to sheath withdrawal) as well as total procedural charges will be recorded on the appropriate eCRFs.

Type(s) and level(s) of sedation provided during the procedure will be recorded on the appropriate eCRF. A single assessment representing the pain associated with balloon inflations during the procedure is recommended to be recorded at or before the time of the patient's discharge assessment. Patients will be instructed to rate the pain they feel

using a numeric pain rating scale (0-10, where 0 indicates no pain and 10 indicates the worst possible pain). A summary of the procedure is given in Table 9.3-1 below.

Table 9.3-1. Procedure requirements

Procedure	
Assessment(s)/ Procedure(s)	Perform angioplasty according to study randomization

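### Procedure time and total charges can include clot removal and central-vein treatment done before randomisation, and section 11.3.2 does not adjust for either, so two secondary endpoints carry avoidable variance

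*Combined protocol and SAP*

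**What the plan says.** Procedure time and procedural cost are secondary endpoints (section 7.5.2).

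- **Time.** Table 7.6-1: "Procedural time (defined as the time from needle entry for intervention to sheath withdrawal) will be assessed after angioplasty with the study device". Section 9.3 repeats the clock and records it beside the bill: "Total procedure time (defined as the time from needle entry for intervention to sheath withdrawal) as well as total procedural charges".
- **Cost.** Table 7.6-1: "Procedural charges and cost-to-charge ratio assessed after submission of UB-04 or CMS-1500 forms". No split of charges by stage of the procedure is described.
- **Randomisation.** Section 9.1: "Once baseline angiography is complete and patient eligibility is confirmed, patients will be randomized". Table 9.1-1 lists central-vein treatment, thrombosis pre-treatment and guidewire crossing ahead of the randomisation step.
- **Pre-treatment.** Section 9.1: "Pre-treatment for thrombosed dialysis access circuits may be performed (e.g., thrombectomy or thrombolysis) prior to enrollment in the study". Central venous lesions over 50% "must be treated successfully prior to treatment of the study lesion". Exclusion 12 in section 8.0 allows this within the study procedure.
- **Enrolment.** Section 9.2: "Patients are considered enrolled in the study once the balloon catheter is first introduced into the patient's body".
- **Analysis.** Section 11.3.2 uses one-sided t-tests, or nonparametric methods if assumptions fail. Regression on the stratification factors is reported only where significance is found. Holm controls the family of secondary endpoints at 0.05. No SD, effect size or power is given for time or cost.

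**The concern.** The assigned balloon can change only what happens after allocation. A patient who first needs a clot removed or a central vein opened has a longer and dearer procedure in either arm, for reasons settled before the arm is known. If that work is counted and not adjusted for, it widens the standard error of both comparisons. These are the endpoints meant to show whether avoiding adjunctive treatment saves time and money. Both pre-treatments are known before randomisation, so the lost precision could be partly recovered at little cost.

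**Working it through.** **Step 1: can the work fall inside the measurement?** Three texts bear on this.

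- Exclusion 6 bars any access-circuit intervention in the 30 days before enrolment. A separate earlier thrombectomy would conflict with it, so the pre-treatment allowed in section 9.1 is most naturally same-session.
- Exclusion 12 says directly that central venous stenosis may be treated during the study procedure.
- Table 9.1-1 puts both ahead of randomisation.

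So a clock opened at needle entry can include them, and so can a procedure total on a billing form. How often is unknown; Table 9.1-1 makes both conditional on need.

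**Step 2: the plan's own figure.** There is none for time or cost. The only sizing statement (section 11.1: 125 lesions per group, 5% v 15%, 80% power) is for the primary endpoint. It reproduces with a one-sided Fisher exact test (79.8% at 125 per group) but has no bearing here.

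**Step 3: loss of power as a function of added SD.** Inputs: 100 patients per arm (section 11.1) and a one-sided 0.05 test before Holm. Assumed: post-randomisation SD of 1, and independent pre-randomisation work with SD r. Then

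total SD = √(1 + r²); power = Φ(δ / (total SD × √(2/100)) − 1.645).

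Set δ to give 80% at r = 0: δ = (1.645 + 0.842) × √0.02 = 0.352 SD.

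| r | Total SD | Power at δ = 0.352 | Difference detectable with 80% power |
|---|---|---|---|
| 0 | 1.000 | 80% | 0.35 |
| 0.25 | 1.031 | 78% | 0.36 |
| 0.5 | 1.118 | 72% | 0.39 |
| 1 | 1.414 | 55% | 0.50 |
| 2 | 2.236 | 30% | 0.79 |

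A true difference of 0.8 SD keeps 99% power at r = 1 and 81% at r = 2. If the Holm family is the six bullets of section 7.5.2, the first step tests at 0.05/6 = 0.0083 (critical value 2.394). Power for δ = 0.352 at r = 0, 0.25, 0.5 and 1 is then 54%, 51%, 43% and 26%.

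**Step 4: the same in terms of frequency.** If a fraction f of patients has pre-treatment adding m SDs, variance is multiplied by 1 + f(1 − f)m².

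- f = 5%, m = 1: 1.0475, power 78%.
- f = 10%, m = 2: 1.36, power 69%.
- f = 30%, m = 3: 2.89, power 43%.

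**Step 5: what yes/no covariates recover.** All times are assumed: post-introduction SD 15 min; baseline work-up SD 8; clot removal 40 (SD 20) min in a fraction p; central-vein treatment 15 (SD 8) min in a fraction c; true saving 5 min. The total variance is

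15² + 8² + [400p + 1600p(1 − p)] + [64c + 225c(1 − c)].

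The covariates remove the terms 1600p(1 − p) and 225c(1 − c). At p = c = 10%:

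- Unadjusted: 225 + 64 + 184 + 26.65 = 499.65, SD 22.4, power 47%.
- Adjusted: 499.65 − 144 − 20.25 = 335.4, SD 18.3, power 61%.
- Post-introduction time alone: SD 15, power 76%.

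In this example the covariates recover about half of the loss (14 of 29 points). The rest comes from work-up and the varying length of pre-treatment.

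**The case against.** Several objections have force.

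- **No bias.** Work done before randomisation is balanced in expectation, and the type I error holds. Chance imbalance in a few long cases is not a second harm; it is the sampling variance already in the standard error. This stands.
- **Every input is assumed.** It stands too: the loss may be trivial.
- **The nonparametric fallback.** A minority of long cases gives right-skewed data, for which section 11.3.2 would plausibly turn to a rank test. Simulating the Step 5 inputs with 90 per arm and 5%/5%, 10%/10% and 20%/15% pre-treated gave about 55%, 49% and 42%, against 51%, 44% and 37% for the t-test. It recovers part of the loss, not all.
- **Whole-procedure time is a legitimate outcome.** Section 7.5.4 chose the secondary endpoints for similarity to the literature and other studies. A clock from first balloon introduction would also drop any arm-dependent time between randomisation and introduction, such as device preparation. This is a good reason not to replace the endpoint.
- **Needle entry for intervention is not defined further.** It could mean access for the study angioplasty only, and Appendix B lists baseline angiography as pre-procedure. So inclusion of all earlier work is possible, not certain.

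A reader might also infer three stronger points that the documents do not support. Charges do not start at needle entry: they come from billing forms and have no clock. A true difference is not necessarily buried, as the 0.8 SD case shows. And Table 7.6-1 does not contradict itself by assessing time after angioplasty. That phrase most naturally says when the value is recorded, as in the cost row, and section 9.3 repeats the clock without it.

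**Conclusion.** The point holds as one of efficiency. Procedure time and total charges can include same-session clot removal and central-vein treatment completed before randomisation, and the planned analysis adjusts for neither. The estimated differences remain unbiased. The power loss on these two secondary endpoints runs from trivial to substantial: 80% becomes 78%, 72% or 55% for added SDs of 0.25, 0.5 or 1 times the post-randomisation SD. These figures assume 100 per arm, a one-sided 0.05 test before Holm, and pre-randomisation work independent of later time. The documents supply none of the SDs, effects or frequencies needed to say where in that range the trial lies. The primary endpoint is untouched.

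**What to change.** In section 11.3.2, add thrombosis pre-treatment (yes/no) and central-vein treatment (yes/no) as prespecified baseline covariates, with the stratification factors, in the procedure-time and cost comparisons. Report that adjusted comparison whatever the covariates' significance, and name it as the one entering the Holm procedure; otherwise the gain is not used.

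Word both eCRF fields as performed before randomisation. The text of section 9.1 fixes these treatments only relative to enrolment or study-lesion treatment; it is Table 9.1-1 that places them before randomisation, and adjustment is safe only for facts settled by then.

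Keep needle-to-sheath time as the defined endpoint. State which needle entry starts the clock and that the time includes adjunctive treatment. Also record the time of randomisation or of first balloon introduction, so that time from that point to sheath withdrawal can be reported as a supporting analysis. Randomisation is the cleaner start, because it leaves out nothing that could depend on the arm.

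The cost is two eCRF fields, one clock time and a slightly more complex analysis. Eligibility, treatment and sample size do not change.

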5.0 Background Information

The safety and performance of the Enforcer balloon were assessed through a series of nonclinical tests performed in accordance with verified methods and procedures to maintain the integrity of the results. The testing results provide reasonable assurance that the potential risks associated with the use of the device have been mitigated to an acceptable level. Additionally, conventional balloon angioplasty is a standard treatment for dialysis access dysfunction and several clinical evaluations have been performed and reported in literature, which assess safety and performance of angioplasty using different balloon technologies (e.g., conventional balloons, high pressure balloons, cutting balloons).¹

A prospective, single-arm, single-center clinical evaluation of the Enforcer balloon was previously conducted to evaluate the treatment of AV access stenoses.² The study evaluated the treatment of 39 AV fistula lesions in 28 patients who were treated with 37 Enforcer balloons; patients were followed for 6 months post-procedure. Device success, defined as < 30% residual stenosis immediately following treatment was 64.1% (25/39). Similarly, 92.3% (36/39) of lesions were reduced to < 50% residual stenosis. Overall, treatment with the Enforcer balloon led to a reduction in the average percent diameter stenosis of the treated lesion from 66.3% pre-procedure to 23.7% post-procedure. The average maximum inflation pressure required was 12.3 atm. Only one lesion required adjunctive treatment following angioplasty with the study balloon, indicating that

clinically relevant luminal gains can be achieved with the study device alone, without the need for a high pressure balloon or other additional therapies.

Following the study procedure, all patients could resume normal dialysis. The Kaplan-Meier estimates for patency at 90 days and 6 months were 62.0% and 25.1%, respectively. The rate of access site complications were low (1/28; 3.6%). Overall, the data supported the safety of the Enforcer balloon for the treatment of stenotic lesions in mature native AV hemodialysis access circuits.

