6.2 Anticipated Clinical Benefits

Percutaneous transluminal angioplasty of a stenosed lesion in an AV access circuit could result in a resumption of normal hemodialysis.

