9.4 Follow-up

Patient medical records will be reviewed through 90 days post-procedure for assessment of adverse events and patency (including reintervention or abandonment of the AV dialysis access site). Adverse event reporting will be limited to those events listed in Section 9.6: Adverse Events. Events occurring after 90 days post-procedure will not be collected. Clinical success will be determined, and is defined as resumption of successful dialysis for at least one session. The follow-up requirements are summarized in Table 9.4-1.

Table 9.4-1. Follow-up requirements

90 Day Follow-up	
Timing	Through 90 days following the study procedure
Type	Chart Review
	Record if patient received at least one successful hemodialysis treatment after the study procedure
	Record adverse events (including, but not limited to, reintervention or abandonment of the study access circuit; refer to section 9.6: Adverse events for a list of reportable events)

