APPENDIX D Definitions

Adjunctive Therapy: Additional treatment necessary for achievement of clinical success immediately following treatment with the study device (Enforcer balloon) or control device (conventional balloon angioplasty). Adjunctive therapies may include high-pressure balloon angioplasty, cutting balloon angioplasty, stents or stent graft.

Adverse Event: Any untoward medical occurrence, unintended disease or injury, or untoward clinical signs (including abnormal laboratory findings) in patients, users, or other persons, whether or not related to the investigational medical device. Refer to Section 9.6: Adverse Events for a list of reportable events.

Anatomic Success: Residual stenosis less than 30% within the treated lesion following the study procedure (including adjunctive therapy).

Arteriovenous (AV) Hemodialysis Access Circuit (also Access Circuit, Dialysis Access Circuit):

- AV Fistula - The vascular conduit beginning from the arterial inflow (2 cm upstream from the AV anastomosis) and ending at the confluence of the cephalic and axillary veins.
- Graft – The vascular conduit beginning from the arterial inflow (2 cm upstream from the artery-graft anastomosis) and ending at the confluence of the cephalic and axillary veins.

AV Hemodialysis Access Circuit, Mature: Native fistula has been successfully used for at least one hemodialysis treatment. Grafts included in the study will have also been successfully used for at least one hemodialysis treatment.

Clinical or physiological abnormalities which indicate dialysis access dysfunction:

Abnormalities may include the following:

- Decreased access blood flow (e.g., <600ml/min, decrease in flow)
- Elevated venous pressure
- Decreased dialysis dose (Kt/V)
- Abnormal physical exam

Clinical Success: Resumption of normal dialysis for at least one session.

Conventional Angioplasty Balloon: A balloon catheter having a rated burst pressure less than 25 atmospheres.

Device Deficiency: Inadequacy of a medical device with respect to its identity, quality, durability, reliability, safety, or performance.

Device Success: Residual stenosis less than 30% within the treated lesion immediately after angioplasty with the study device (Enforcer or conventional angioplasty balloon).

Dissection: Linear filling defect due to disruption of the intima, staining within the vessel wall.

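### The clinical success definition does not exclude a dialysis session through another access, or one that follows reintervention in or abandonment of the study circuit

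*Combined protocol and SAP*

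**What the plan says.** Clinical success is listed in Section 7.5.3 as an additional measure. It is defined three times:

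- Table 7.6-1: "Resumption of successful hemodialysis for at least one session from chart review through 90 days".
- Section 9.4: "Clinical success will be determined, and is defined as resumption of successful dialysis for at least one session".
- Appendix D: "Resumption of normal dialysis for at least one session".

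The item that produces the data is in Table 9.4-1: "Record if patient received at least one successful hemodialysis treatment after the study procedure".

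Two other texts bear on how these should be read. Section 6.2 describes the hoped-for benefit: "Percutaneous transluminal angioplasty of a stenosed lesion in an AV access circuit could result in a resumption of normal hemodialysis". The Appendix D entry for a mature circuit reads "Native fistula has been successfully used for at least one hemodialysis treatment", with the same condition for grafts.

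Section 7.5.4 presents the additional measures as indicators of device effectiveness, and Section 11.3.3 applies the same between-group analysis strategies to them.

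**The concern.** A measure of whether the procedure restored a usable access should fail when the treated circuit is lost, or needs another intervention, before it has been used again. As written, the definition looks at whether the patient dialysed, not at whether the treated circuit was dialysed through. The patients who could be scored wrongly are early clinical failures, which are the cases this measure exists to detect. If they are counted as successes, the reported rate in each group is too high, and a difference between the groups in very early access failure would not show in this measure.

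**Working it through.** The plan gives no expected rate, sample size or power for clinical success, so there is no figure to reproduce. The check compares the texts.

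**Step 1. The four texts side by side.**

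| Place | Word for an adequate session | Time window | Access named | Ordered against reintervention or abandonment |
|---|---|---|---|---|
| Table 7.6-1 | *successful* | through 90 days | no | no |
| Section 9.4, text | *successful* | 90-day chart review, from context | no | no |
| Table 9.4-1, item | *successful* | after the procedure, 90-day chart review | no | no |
| Appendix D | *normal* | none | no | no |

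Neither *successful* nor *normal* is defined.

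**Step 2. Where the plan does name the circuit.** The next row but none of the clinical success wording shows the contrast: the primary patency row of Table 7.6-1 refers to the access circuit, and the maturity definition refers to use of the fistula or graft itself. The clinical success item has the patient as its subject.

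**Step 3. Apply the Table 9.4-1 item literally.**

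- The circuit occludes before any session, is reintervened on, and the first session follows: recorded as success.
- The circuit is abandoned before any session and the patient dialyses through another access: recorded as success.
- One good session through the circuit, then restenosis: recorded as success. This is correct for a one-session measure, and the later loss appears under primary patency.

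Only the first two cases are at issue.

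**Step 4. Can the analysis correct it?** Section 9.5 allows reintervention, and Section 10.0 lists neither reintervention nor abandonment as an end of participation, so the chart review continues. Section 9.6 captures onset dates of adverse events, including restenosis or occlusion that leads to either. But the plan lists no date for the dialysis session and no access route. The order of session and failure, and the route used, cannot be established from the items listed.

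**Step 5. Size.** Let *f* be the proportion of patients whose treated circuit fails before it is used again and who still have a session by day 90. With about 200 patients (Section 11.1), the number recorded wrongly is 200 × *f*; for *f* = 1% this is 200 × 0.01 = 2. The documents give no value for *f*.

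The earlier single-arm study in Section 5.0 does not supply one. It reports "Following the study procedure, all patients could resume normal dialysis", which is 28 of 28, beside Kaplan-Meier patency of 62.0% at 90 days. That leaves 100 − 62.0 = 38.0% without patency, or 0.38 × 28 = 10.6 patients if the estimate applies per patient (the unit is not stated). These losses could all have come after a good session through the treated circuit, so the contrast does not show that anyone was misclassified.

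**The case against.** The strongest reply is that the texts are silent rather than permissive. Section 6.2 links resumption to treatment of the access circuit, and the maturity definition uses *successfully* for use of the circuit itself, so a sensible site might read the item as meaning the treated access. The eCRF and its instructions are not in the documents. This stands in part: the right statement is that the definition does not exclude these sessions. But Section 6.2 is benefit text, not a scoring rule, and nothing in the item directs a site to the narrower reading.

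The second reply is that access failure is captured elsewhere: primary patency, the secondary safety measures (rupture, tears, reintervention/patency) and reportable events. This stands, and it limits the consequence. It does not make the clinical success rate correct.

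A reader might infer more than the documents support:

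- *That early access failures in general are scored as successes.* Failures after one good session are properly left to primary patency.
- *That the measure is nearly always positive.* This is plausible, but it rests on 28 of 28 patients in one single-arm study. The exact two-sided 95% lower bound is 0.025^(1/28) = 87.7%, which leaves room for a failure rate of up to 12.3%.
- *That resumption is already met at baseline.* Eligibility requires dysfunction, not interrupted dialysis, but no proportion still dialysing is given. Section 9.1 also admits thrombosed circuits after pre-treatment, for which resumption is a real test. Maturity concerns use before entry; clinical success concerns a session afterwards.
- *That only death or withdrawal could count as failure.* Section 11.4 specifies complete-case analysis for measures other than the primary endpoint, so such patients may be missing instead.

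**Conclusion.** The concern holds in a limited form. The three definitions and the Table 9.4-1 item leave open the access used and the order of the session relative to reintervention or abandonment. A patient whose treated circuit fails before it is used again can therefore be recorded as a clinical success, and the listed data would not allow this to be put right. The conclusion assumes that sites complete the item as it is worded.

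The number affected cannot be estimated from the documents. Clinical success is outside the primary and secondary endpoints, and no hypothesis or sample size rests on it. A reader might infer a threat to the primary endpoint because Appendix D describes adjunctive therapy by reference to clinical success. Table 7.6-1, however, assesses the primary endpoint by what was used during the procedure, which does not depend on the 90-day item. The point is still worth correcting before chart review, because the plan treats the measure as an indicator of effectiveness and compares it between groups.

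**What to change.** Use one definition in Table 7.6-1, Section 9.4 and Appendix D: at least one successful haemodialysis session through the study-treated access circuit, after the study procedure and before any reintervention for restenosis or occlusion in that circuit, or its abandonment. Limiting the reintervention clause to restenosis or occlusion matches the primary patency definition; the Appendix D term reintervention alone covers any intervention in the circuit and would count unrelated ones as failures.

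Replace *successful* and *normal* with a single term. Have Table 9.4-1 record the date of the first session and the access used.

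The cost is wording in three places and one or two added eCRF fields, completed from the chart review already planned. The reported success rate may be slightly lower. If the change comes after some reviews are complete, those charts would have to be reopened.
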